6.4.2. Remote Enrolment Procedures

The Informed Consent form may be electronically distributed (i.e. email or fax) to potential participants, and the investigator or delegated study personnel may remotely review the Informed Consent form content and address initial questions via phone or video conferencing (e.g. Zoom). Remote Informed Consent review is optional to investigators and subjects and is supplemental to the in-person informed consent process. In all cases an in-person review of the Informed Consent form, as described in the above enrolment procedures, must occur at the scheduled in-person screening visit. Each investigational site will determine if the Informed Consent signing may be conducted remotely using electronic signature (e.g. DocuSign), or if all Informed Consent forms shall be signed during the in-person screening visit.

6.4.3. Study Procedures

At the first visit after informed consent has been given, the investigator will review the subject's medical history, ocular history (including concomitant treatments), demographics and contact lens wear history. The subject will complete a baseline symptoms questionnaire. A series of routine optometric assessments and tests will be conducted to evaluate the subject's ocular health and refractive status. This will include measurement of manifest spherocylindrical refraction, best sphere refraction and resultant visual acuity, keratometry, and biomicroscopy (slit-lamp examination). Once it has been verified that the subject meets the inclusion / exclusion criteria the test lens parameters will be determined based on Rx. The lens parameters will be recorded, and the subject will be randomized to receive the test or control lenses, which will be dispensed from a stock at the site. After insertion of the study lenses the fit and visual acuity will be evaluated and an over-refraction with visual acuity will be performed. The subject will be educated on safe contact lens use, and will be instructed to wear the study lenses on a one-month replacement schedule for at least 6 hours a day for a minimum of 5 days per week. The subject will be provided with Biotrue or ClearCare for routine cleaning, disinfection and storage; and will be educated on the daily care regimen for the study lenses. At the conclusion of the visit, follow-up visits will be scheduled.

There will be five scheduled follow-up visits during the treatment period at the following intervals: 7 days, 14 days, 30 days, 60 days, and 91 days. During these follow-up visits any changes to medical history will be reviewed, the subject will complete a symptom questionnaire, and a series of routine optometric assessments

and tests will be conducted to evaluate the subject's ocular health and refractive status. This will include measurement of manifest spherocylindrical refraction, best sphere refraction and resultant visual acuity, visual acuity with contact lens, over-refraction with visual acuity, and biomicroscopy (slit-lamp examination) including evaluation of the fit and surface of the study lens. Additionally, on the 91 day visit keratometry will be recorded. At the conclusion of each visit, the subject will be instructed to continue to wear and care for the study lenses, and the next follow-up visit will be scheduled. Additional supply of study lenses and care solution will be dispensed on Day 30 and Day 60 visits (or as needed). At the completion of the 91 day visit the subject will be discharged from the study and a Trial Exit Form will be completed.

6.4.4. Remote Study Procedures

With consideration for the current global pandemic (COVID-19), the follow-up study visit procedures listed below may be conducted remotely (via telephone or video conference) and recorded on the eCRF to reduce physical exposure time between the subjects and study personnel:

- Questionnaires (vision/comfort/handling/wear time/symptoms)
- Changes in medication (concomitant treatments) and health history
- Scheduling

All remote reporting of questionnaires must occur on the same calendar day of the scheduled in-person visit and must be prior to the visit. Scheduling may occur remotely at any time between visits. Any eligible procedures not conducted remotely prior to the visit shall be conducted during the in-person visit. If remote reporting was conducted and the subject is not present for the in-person visit on the same calendar day, then the completed procedures shall be reported again on the date of the actual in-person visit. The utilization of remote reporting procedures in this study is optional to investigators and subjects.

All other study visit procedures not identified in this section (6.4.4) or section 6.4.2 shall be conducted with the subject physically present during the in-person clinic visit.

6.4.5. Subject Instructions

The subjects will be provided with a patient instruction guide for the Qualis Silicone Hydrogel Soft Contact Lens. All study contact lens care solutions and control contact lenses will be dispensed with a package insert/patient instructions.

6.4.6. Examination Schedule

There will be a total of six (6) scheduled study visits:

- Visit 1: Screening/Enrolment/Baseline/Lens Dispensing
- Visit 2: Day 7 (5 to 9 days after dispensing)
- Visit 3: Day 14 (12 to 16 days after dispensing)
- Visit 4: Day 30 (25 to 35 days after dispensing)
- Visit 5: Day 60 (55 to 65 days after dispensing)
- Visit 6: Day 91/Study Exit (91 to 101 days after dispensing)

6.4.7. Clinical Parameters

All procedures for the study are routine procedures that are performed as part of standard clinical care.

Visit 1: Screening/Enrollment/Baseline/Lens Dispense

Investigators will adhere to the following routine:

- Explanation of the study*
- Signing of the consent form*
- Assignment of the subject identification number
- Demographics and ocular history questionnaire
- Concomitant treatments
- Habitual contact lens wearing history
- Comfort, vision, and handling questionnaire
- Symptoms questionnaire
- Manifest spherocylindrical and best sphere refraction
- Visual acuity (LogMAR) with spectacle refraction
- Keratometry
- Slit lamp biomicroscopy examination to evaluate ocular integrity (limbal redness, bulbar redness, corneal staining, corneal infiltrates, other findings; GPC, vascularization, edema/striae, microcysts, pinguecula, etc.)
- Review of inclusion and exclusion criteria / eligibility determination
- For subjects that fail to meet enrolment criteria, document the screening failure
- For subjects that meet the study criteria document their enrolment, assign a subject ID, and apply the subject ID to the Subject Randomization List. Determine the applicable contact lens power based on Rx and dispense lenses.

~ **INSERT** study lenses and wait 5 minutes~

- Visual acuity (LogMAR) and over-refraction with dispensed contact lenses
- Slit lamp evaluation for contact lens fit and contact lens surface quality

- Instruction on contact lens care and use
- Adverse event identification and reporting
- Device deficiency reporting
- Protocol deviation reporting
- Schedule follow up visit(s)*

* May be completed remotely.

Visit 2, 3, 4, and 5: Follow Up Visit – Day 7, Day 14, Day 30, and Day 60.

Investigators will adhere to the following routine:

~ subject is instructed to wear study lenses at the visit ~

- Update medical history/concomitant treatments questionnaire*
- Comfort, vision, and handling questionnaire*
- Symptoms questionnaire*
- Visual acuity (LogMAR) and over-refraction with dispensed contact lenses
- Slit lamp evaluation for contact lens fit and contact lens surface quality

~ REMOVE study lenses~

- Slit lamp biomicroscopy examination to evaluate ocular integrity (limbal redness, bulbar redness, corneal staining, corneal infiltrates, other findings; GPC, vascularization, edema/striae, microcysts, pinguecula, etc.)
- Manifest spherocylindrical and best sphere refraction
- Visual acuity (LogMAR) with spectacle refraction
- Keratometry
- Adverse event identification and reporting
- Device deficiency reporting
- Protocol deviation reporting
- Additional supply of one-month study lenses dispensed (Day 30 and Day 60 visits)
- Additional care product dispensed as needed
- Schedule follow up visit(s)*
- For discontinued subjects, complete Exit Form and collect all study lenses from the subjects then discharge subjects from the study

* May be completed remotely.

Visit 6: Follow Up Visit – Day 91 – Final Treatment/Exit Visit

Investigators will adhere to the following routine:

~ subject is instructed to wear study lenses at the visit ~

- Update medical history/concomitant treatments questionnaire*
- Comfort, vision, and handling questionnaire*
- Symptoms questionnaire*
- Visual acuity (LogMAR) and over-refraction with dispensed contact lenses
- Slit lamp evaluation for contact lens fit and contact lens surface quality

~ REMOVE study lenses~

- Slit lamp biomicroscopy examination to evaluate ocular integrity (limbal redness, bulbar redness, corneal staining, corneal infiltrates, other findings; GPC, vascularization, edema/striae, microcysts, pinguecula, etc.)
- Manifest spherocylindrical and best sphere refraction
- Visual acuity (LogMAR) with spectacle refraction
- Keratometry
- Adverse event identification and reporting
- Device deficiency reporting
- Protocol deviation reporting
- Collect all study lenses from the subjects
- Complete Exit Form and discharge subjects from the study

* May be completed remotely.

Refer to the table in section 6.1.4 for the clinical parameters and testing frequency.

Some procedures (e.g. keratometry, questionnaires) may be performed independently by office technicians / clinical research associates or optometrists under the investigator's supervision, after training into the protocol and qualification, using methods described in Appendix 2. When possible, each subject's measurements will be performed by the same operator or technician, using the same piece of equipment at the site.

Additional examinations (such as photography etc.) may be conducted if deemed appropriate.

Interim Visits

Subjects may return for interim visits between scheduled visits as necessary. The Follow Up Visit Form should be completed for all interim visits (specify “unscheduled visit” on the eCRF).

- Adverse Event Related Interim Visits: when a potentially significant adverse event occurs the Investigator should schedule frequent follow up to monitor and thoroughly document the duration of the event. The Clinical Monitor or Medical Monitor should be consulted when determining a follow up schedule to the adverse event.
- Loss of BCVA: in the case of a specific event where the subject’s visual acuity is reduced by ≥ 10 letters (LogMAR), a follow up visit should be scheduled within 3 days of the event. If the visual acuity loss persists at follow up, ongoing follow up visits should be scheduled within 3 days until the visual acuity loss has resolved or the Investigator determines the condition is stable.
- Lost or broken lenses: in the case where the subject requires replacement of a lost or broken lens an interim visit will be scheduled and the following procedures will be conducted at the visit (and recorded on the follow up visit eCRF):
 - o Visual acuity (LogMAR) and over-refraction with dispensed contact lenses
 - o Slit lamp evaluation for contact lens fit and contact lens surface quality
 - o Adverse event identification and reporting
 - o Device deficiency reporting
 - o Protocol deviation reporting

6.4.8. Study Completion Procedures

A study exit form must be completed for all subjects.

Subject Completion:

Subjects are considered to have completed the study if they have completed follow-up examinations through the 91-day study period and when all of the study procedures have been completed. All completed subjects’ data will be considered evaluable unless a significant protocol deviation was reported. Written justification will be required for the use of data in the evaluation of the safety and/or efficacy of study product from any subject found to have a protocol deviation.

Subject Discontinuation:

Possible reasons for discontinuation include:

1. Screen Failure – the subject does not meet the protocol specified inclusion criteria or has one or more of the exclusion criteria present.
2. Adverse Event – the subject has been reported to have an adverse event and was discontinued due to the adverse event.
3. Subject Decision – the subject decides for whatever reason to exit from the study. The reason must be recorded in the comments section of the Exit Form.
4. Investigator, Sponsor or IRB Decision – the subject is exited from the study based on a decision by the investigator the Sponsor or the reviewing IRB. The reason for discontinuation must be recorded in the comments section of the Exit Form.
5. Protocol Violation – the subject or the investigator is repeatedly found to be in violation of the study protocol.

Subjects may be discontinued from the study at the discretion of the investigator only for reasons related to the study treatment regimen that would jeopardize the subjects' health and/or welfare if they were to continue in the study.

Discontinued subjects will be considered to have completed the study and should not be replaced. However, every effort will be made to follow discontinued subjects to obtain as much follow-up data as possible regarding the subject's current visual status until the planned end of the study period.

NOTE: The Investigator will immediately (within 2 working days) notify Monitor/CRO if a subject discontinues from the study.

Subjects Lost to Follow-up:

Subjects may be lost to follow-up from the study for non-treatment related reasons. Reasons for loss to follow-up include, but are not necessarily limited to:

- 1) voluntary withdrawal from the study by the subject;
- 2) subject has moved from the area; or
- 3) subject is unwilling or unable to return for follow-up.

The reason for loss to follow-up will be recorded on the appropriate case report form. Every effort should be made to contact the subject in an effort either to get the subject back into compliance with the protocol or to obtain as much follow-up data as possible regarding the subject's current refractive status and ocular health.

Data to be collected:

Visual acuity and slit lamp examination should be completed for each subject at the time of discontinuation.

Any follow-up required:

Subjects who are to be exited from the study for an adverse event must be followed until the condition has resolved, returned to pre-study status or warrants no further follow-up before being discontinued from the study.

Unscheduled visits must be conducted until the condition has resolved, returned to pre-study status or warrants no further follow-up.

If the resolution has not occurred within 6 weeks after the study end-date, the subject will be exited from the study but must continue to be followed by the investigator until the condition has resolved, returned to pre-study status or warrants no further follow-up.

Medical Care Post Study Completion:

No continuing medical care will be provided for subjects after completion except for the care required to follow-up and resolve a device related adverse event that started during the study.

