7. STATISTICAL CONSIDERATIONS

The CRO will manage data analysis and reporting. Subject characteristics and study conduct summaries will be reported—including tables such as a subject disposition table, demographics and baseline characteristics tables (including age, gender, baseline refraction, lens wear experience), summary table of screen failures by reason, accountability of eyes enrolled, and subjects excluded from key analysis sets.

All descriptive summary statistics will be displayed with n and % for categorical data, and with mean, standard deviation, median, minimum, and maximum for continuous data. The unit will be eye. Tables will be presented by treatment and overall. Slit lamp findings will be presented by all study visits, tabulated by eyes and incidence rate for completed test lens group, completed control lens group, discontinued test lens group and discontinued control eyes group. Primary and secondary outcomes will be analyzed by descriptive statistics only. As such, there are no statistical hypotheses to be tested.

Trend analysis profile will be provided following directions provided in the FDA guidance *Premarket Notification [510(k)] Guidance Document for Class II Daily Wear Contact Lenses*. All participants who meet the eligibility criteria, adhere to the protocol, and successfully complete the full study assessment will be available for the per-protocol analysis. Subjects with missing data will be included in the analysis unless there is some non-response-related reason to exclude them, such as a protocol violation/invalid data. Data from all enrolled subjects will be used for reporting of adverse events or other safety related outcomes.

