- Logistical or administrative aspects of the study (e.g., study subject missed appointment, change in appointment date);
- Inadvertent deviation in specific research intervention procedures or timing of the research intervention which would *not* impact upon the safety or efficacy of the study-related intervention or upon the experimental design (e.g., missing a measurement during a session that is not considered critical for the study).

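### Section 6.4.8 makes non-use the default for safety data from any subject with a protocol deviation, which conflicts with the all-enrolled safety rule in Section 7

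*Combined protocol and SAP*

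**What the plan says.** Section 6.4.8 (Study Completion Procedures) makes two statements in succession under subject completion. The first is: "All completed subjects’ data will be considered evaluable unless a significant protocol deviation was reported". The second, which concerns anyone with a recorded deviation, is: "Written justification will be required for the use of data in the evaluation of the safety and/or efficacy of study product from any subject". The first depends on a *significant* deviation. The second has no such qualifier and names safety as well as efficacy.

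Section 7 (Statistical Considerations) sets the safety population: "Data from all enrolled subjects will be used for reporting of adverse events or other safety related outcomes". It makes no exception for deviations. The same section keeps subjects with missing data in the analysis "unless there is some non-response-related reason to exclude them, such as a protocol violation/invalid data". It also tabulates slit-lamp findings at all visits, by lens, separately for completed and discontinued groups.

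Section 14, on reporting procedures, commits the final clinical report to all adverse events, whatever their classification.

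Section 10 divides deviations into major and minor and has no class called significant. Its examples of minor deviations include "study subject missed appointment, change in appointment date".

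Section 6.1.3 lists ocular adverse events and visual acuity as the primary outcomes. Section 6.1.1 describes the trial as open-label. Section 6.3.4 counts as enrolled everyone who consents and proves eligible at screening, whatever happens afterwards.

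**The concern.** A safety population should not depend on whether a subject kept to the protocol. Section 6.4.8 starts from the opposite position: once a deviation is recorded, the subject's data need a written case before they count towards safety. Because a moved appointment is a deviation under Section 10, the rule can reach many subjects for reasons unrelated to the lens.

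Section 7 plans descriptive statistics only, with no hypothesis test. The tabulated rates are therefore the evidence offered for substantial equivalence, with at most 50 subjects on the test lens and 25 on the control. In groups of that size, one or two subjects in or out visibly change a rate. If inclusion is settled case by case while lens and outcome are known, the rates can be biased, and not necessarily equally in the two arms. Type I error and power are not at issue, since the plan tests nothing.

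**Working it through.** The plan gives no figure to reproduce here: there is no deviation rate, and no alpha, power or margin. The check is a comparison of texts, followed by two illustrations on assumed inputs.

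**1. The rules side by side**

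| Place | Who it covers | Effect on safety data |
|---|---|---|
| 6.4.8, first sentence | Completed subjects | Evaluable unless the deviation is significant (undefined) |
| 6.4.8, second sentence | Any subject with any deviation | Not used without written justification |
| 7 | All enrolled subjects | Used, with no exception |
| 14 | All adverse events | Reported, with no exception |

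The second row sets a default opposite to the third. The first two rows use different thresholds in adjacent sentences. No section says which rule prevails.

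**2. How far the 6.4.8 sentence reaches.** It stands under subject completion, but its words are any subject, and 6.4.8 goes on to treat discontinued subjects as having completed. One listed reason for exit is that "the subject or the investigator is repeatedly found to be in violation of the study protocol", so a subject could come under the rule through the investigator's conduct. The Adverse Event Form in Appendix 3 also instructs that a Protocol Deviation Report be filed when a subject with an adverse event continues in the study. That may be a slip in the form. Read literally, it puts every such subject under the 6.4.8 default.

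**3. What is left unspecified.** The documents do not say who writes or approves the justification, on what criteria, by when, or without knowledge of lens. The follow-up eCRF shows the study lens type.

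**4. How many subjects might need a justification.** Assume each of the five follow-up visits independently carries probability q of some deviation. The share with at least one is 1 − (1 − q)^5, applied to the 75 planned subjects:

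- q = 2%: 1 − 0.98^5 = 0.096; × 75 = 7.2, about 7
- q = 5%: 1 − 0.95^5 = 0.226; × 75 = 17.0, about 17
- q = 10%: 1 − 0.90^5 = 0.410; × 75 = 30.7, about 31

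These are subjects for whom a written note would be required. If deviations cluster in the same subjects, the counts are lower.

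**5. How sensitive a rate is.** Hypothetical, at subject level (Section 7 tabulates by eye), test arm of 50, with exact Clopper-Pearson 95% intervals:

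- 3/50 = 6.0% (1.3% to 16.5%)
- one subject with an event left out: 2/49 = 4.1% (0.5% to 14.0%)
- two left out: 1/48 = 2.1% (0.1% to 11.1%)

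This shows the scale of a possible shift. Nothing in the documents predicts that it would occur.

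**The case against.** The strongest reply is that the specific provisions already protect safety. Section 14 puts every adverse event in the final report, Section 7 uses all enrolled subjects, and slit-lamp findings are tabulated for discontinued subjects too. Section 6.4.8 also asks for acuity and a slit-lamp examination at discontinuation. Against these stands one general sentence in a section on completion, which can be read as the documentation step for the significant deviation mentioned just before it. Writing a justification for every affected subject would satisfy 6.4.8 and Section 7 together.

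Much of this stands. A reader might infer that adverse events could be dropped from the report; Section 14 rules that out. A reader might infer that the sponsor or CRO decides inclusion after seeing the data; the documents name no decision-maker and no timing, so that comes only from silence. Nor does 6.4.8 say that only completed subjects are evaluable; it says that all of them are, subject to its exception. Section 4.2 links complications to non-compliant behaviour, but in the context of using the lens and care product as directed. It does not say that subjects who miss or move appointments have more events.

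What remains is that listing an event does not settle who enters the rate, the denominator, or the slit-lamp and acuity summaries. The narrower reading of 6.4.8 is possible, but its words do not require it.

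**Conclusion.** The conflict is in the text and should be fixed. Section 6.4.8 makes safety data from a subject with any deviation unusable by default, while Section 7 uses every enrolled subject and Section 14 reports every adverse event. The listing of adverse events is safe. Membership of the safety summaries is open to discretion, in an open-label trial with no owner, criteria or timing for the decision.

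The size is unknown because no deviation rate is given. The figures of about 7, 17 or 31 of 75 rest on assumed per-visit rates and on independence between visits. A reader might take them as subjects lost from the analysis; they are subjects needing a justification, and the documents do not support any number excluded.

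**What to change.** In Section 6.4.8:

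- Delete *safety and/or* from the written-justification sentence.
- State that safety data from all enrolled subjects, as in Section 7, are analysed regardless of deviations, completion or reason for exit. This includes the slit-lamp and visual acuity safety summaries. Show subjects never dispensed a lens separately in the accountability table.
- Confine the evaluability rule to the per-protocol set, with a single threshold: deviations that affect the validity of the effectiveness data. Section 10's major class is a poor substitute, because it is built around IRB reporting and includes consent-documentation errors and changes made to remove immediate hazards.
- Document each per-protocol exclusion, with its reason, before arm-level tables are produced. This does not mask anyone in an open-label trial, but it limits choices driven by the comparative results.

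The cost is a short rewording of 6.4.8, with no extra data. The reported safety figures may be slightly less favourable.

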Care Solutions:	The Subjects will be using FDA cleared contact lens care products that are commercially available for silicone hydrogel daily lens maintenance, care and storage. To disinfect the contact lenses daily, Biotrue MPS and Alcon ClearCare Peroxide will be used. A randomization scheme will be provided to the investigational site to randomly assign subjects to one of the two lens care system (Biotrue or ClearCare) in a 1:1 manner. PuriLens Plus Preservative Free Saline will be supplied to subjects for use as needed in conjunction with the daily disinfection system.

Summary of Visit Schedule:	
There will be a total of six (6) scheduled study visits*:
 
Visit 1: Screening/Enrolment/Baseline/Lens Dispensing
 
Visit 2: Day 7 (5 to 9 days after dispensing)
 
Visit 3: Day 14 (12 to 16 days after dispensing)
 
Visit 4: Day 30 (25 to 35 days after dispensing)
 
Visit 5: Day 60 (55 to 65 days after dispensing)
 
Visit 6: Day 91 (91 to 101 days after dispensing)
 
* Interim visits to be undertaken as required

Number of Subjects:	
To ensure a minimum of 50 completed subjects (with 30 completed subjects in the test arm), 75 subjects will be enrolled to participate. Up to fifty (50) subjects will wear the test contact lenses and up to twenty-five (25) subjects will wear the control contact lenses.
 
The number of subjects was determined based on the recommendations in Premarket Notification [510(k)] Guidance Document for Class II Daily Wear Contact Lenses.

Number of Sites:	
A minimum of three (3) sites and five (5) independent investigators will participate in this clinical study. The target subject enrollment at each study site will be equivalent.

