6.1.6. Replacement of Subjects

To ensure a minimum of 50 completed subjects (with 30 completed subjects in the test arm), 75 subjects will be enrolled to participate. Subjects that have dropped out of the study will not be replaced.

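### Section 6.4.8 gives two incompatible completion rules, so it is unclear whether discontinued subjects count toward the target of 50 completers, 30 of them in the test arm

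*Combined protocol and SAP*

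**What the plan says.** Section 6.4.8 of the combined protocol and SAP contains both rules.

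- Under Subject Completion: "Subjects are considered to have completed the study if they have completed follow-up examinations through the 91-day study period", with the further condition that all study procedures are done. The same paragraph makes completed subjects' data evaluable unless there was a significant deviation.
- Under Subject Discontinuation: "Discontinued subjects will be considered to have completed the study and should not be replaced".

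The section also describes two kinds of exit. Discontinuation reason 3, the subject's own decision, applies when "the subject decides for whatever reason to exit from the study". Under the separate heading for loss to follow-up, "Subjects may be lost to follow-up from the study for non-treatment related reasons", and the first reason listed is "voluntary withdrawal from the study by the subject".

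The size target is stated in completers. The Synopsis (1.5) says "To ensure a minimum of 50 completed subjects (with 30 completed subjects in the test arm), 75 subjects will be enrolled to participate", and Sections 6.1.6 and 6.3.6 repeat it. Section 6.1.6 adds "Subjects that have dropped out of the study will not be replaced". Section 7 has slit lamp findings "tabulated by eyes and incidence rate for completed test lens group, completed control lens group, discontinued test lens group and discontinued control eyes group". The Exit Form in Appendix 3 has a yes/no item on whether the subject completed, and separate reason boxes for patient decision and for loss to follow-up.

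**The concern.** One term carries two definitions within one section, and the enrolment target is expressed in that term. If the discontinuation sentence were used to count completers, people who stopped early would count toward the 50 and the 30. The figure in the final report would then overstate how many subjects were observed for three months.

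The exit classes make this worse. A voluntary exit unrelated to treatment fits both the subject-decision reason and the loss-to-follow-up reason. Only the discontinued class is declared to have completed, so the label given to such an exit could decide whether it counts.

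Evaluability is also attached to completed status in 6.4.8, so the second rule blurs who is evaluable.

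**Working it through.** **The two rules set against the other text**

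| Place | 91-day rule | Discontinued = completed |
|---|---|---|
| 6.4.8, Subject Completion | states it | contradicts |
| Section 7, slit lamp groups | fits | leaves no clear line between the completed and discontinued columns |
| Exit Form completion item | fits | the item would not separate discontinued subjects from those seen to day 91 |
| 6.4.8, discontinuation reason 1 (screen failure) | fits | read literally, a screen failure has completed |
| 6.1.6, no replacement | neutral | not needed, since 6.1.6 bars replacement by itself |

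**Inputs from the documents:** 75 enrolled, up to 50 test and up to 25 control; floor of 50 completers, 30 in test; no replacement.

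**The plan's own figure.** The 75 cannot be derived, because no leaving rate is stated. Working backwards, the floor tolerates a loss of 1 − 50/75 = 33.3% overall and 1 − 30/50 = 40% in the test arm. That 50/(1 − 1/3) = 75 is only a consistency check, since the 1/3 comes from the 75.

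**Chance of missing the floor under the 91-day rule.** Assumptions: exactly 50 and 25 enrolled, everyone who stays has all procedures done, and subjects leave independently at the same rate p in both arms. With t test leavers and c control leavers, the floor is met when t ≤ 20 and t + c ≤ 25. Hence

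P(miss) = 1 − Σ (t = 0 to 20) Bin(t; 50, p) × P(Bin(25, p) ≤ 25 − t).

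| Assumed p | Expected completers, 75(1 − p) | Expected in test, 50(1 − p) | P(miss) |
|---|---|---|---|
| 20% | 60 | 40 | 0.2% |
| 25% | 56.25 | 37.5 | 4.0% |
| 30% | 52.5 | 35 | 22.5% |
| 33.3% | 50 | 33.3 | 44.9% |
| 40% | 45 | 30 | 85.7% |

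**The same floor if the discontinuation sentence governed the count.** Completers would be the enrolled minus those classed as lost, so p is replaced by p × s, where s is the share of leavers classed as lost.

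- s = 0 (every leaver classed as discontinued): the count is 75 and P(miss) = 0 at every p.
- s = 0.5 (an assumption): P(miss) is 0.002%, 0.013% and 0.23% at p = 30%, 33.3% and 40%.

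**Boundary example.** Suppose 26 of 75 leave (34.7%). The 91-day rule gives 75 − 26 = 49, and the floor is missed. Under the other sentence, with all 26 classed as lost, the count is also 49. Relabel one of them as a subject decision and it is 75 − 25 = 50, so the floor is met, provided no more than 20 test subjects are classed as lost.

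**The case against.** The strongest reply is that the sentence is a stray administrative remark meaning that participation has ended and the place will not be refilled. There is some support for this. The next sentence opens with a contrast and asks that discontinued subjects still be followed, and 6.4.8 elsewhere uses completion for the end of participation when it discusses medical care afterwards. Enrolling 25 more than the 50 needed makes sense only if leavers are not completers. The Exit Form has a reason box for having finished the visit schedule. Wherever the term is used for counting, it points to the 91-day rule.

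Much of this stands. A reader might infer that the sentence empties the 50/30 floor. The documents do not support that, because nothing says the discontinuation sentence governs the count. Nor would loss to follow-up be the only route to failure: under-enrolment (both arm sizes are upper limits), or subjects who attend day 91 but lack a procedure, could also miss it. A reader might also infer that the per-protocol set or the discontinued slit lamp columns change. They do not, because Section 7 words those separately. The floor is also not the only stated size target, since enrolment of 75, split up to 50 and up to 25, is given too.

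The harm is further limited by reporting. Discontinuations and their reasons are a secondary outcome, Section 7 calls for a disposition table, and the Exit Form records the visit and reason. A reader of the report could largely rebuild the count.

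The reply does not remove the contradiction. The administrative meaning is not written down, and the sentence uses the very term that the section has just defined.

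**Conclusion.** The contradiction is real and the sentence is wrong as written. Its consequence is modest: an ambiguous completer count and uncertainty about evaluability under 6.4.8. The analysis is descriptive with no hypothesis test, so no error rate or power is affected, and no action depends on missing the floor.

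The size depends on a leaving rate that the documents do not give. At 20% or below the 91-day floor is almost always met (miss chance 0.2%), so the choice of rule hardly affects whether the target is reached. From about 30% upward the two rules could give opposite answers on the floor. These figures assume 50/25 enrolled, equal and independent leaving in both arms, and no attenders with missing procedures.

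**What to change.** In Section 6.4.8, replace the sentence with: *Discontinued subjects are not completers and will not be replaced.* State there, or beside the target in 6.3.6, that only subjects who meet the 91-day completion rule count toward the 50 and the 30. Place voluntary withdrawal in one exit class only, and say which Exit Form box it takes.

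The cost is two or three sentences and a matching instruction for the Exit Form, with no new subjects, visits or measurements. The one downside is that the reported number of completers may be lower than under the present sentence.
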